An Open-label Study to Investigate the Efficacy and Tolerability of Aczone Gel, 7.5% in the Treatment of Acne Vulgaris in Men and Women With Skin of Color

[name]

NCT03681470

Document Date: Feb 7, 2022

Protocol Document for 17-01277
Principal Investigator: [name].
Mount Sinai

Brief Summary of Research

Acne vulgaris is a common skin disease characterized by inflammatory papules, pustules, and comedones that is prevalent in men and women of color. Research has demonstrated that Aczone[®] (dapson) gel, 7.5% used once daily is effective, safe, and well-tolerated for the treatment of acne in both men and women; however, no data is available regarding its efficacy and safety in skin of color (SOC). The current study aims to investigate the therapeutic impact of Aczone gel 7.5% in SOC males and females ages 18 and older with acne vulgaris. The study will also evaluate the impact of Aczone[®] gel on hyperpigmentation and PIH of the face.

Objectives

The purpose of this study is to evaluate the safety and efficacy of Aczone[®] gel, 7.5% administered once daily for 24 weeks in males or females with skin of color (SOC), defined as Fitzpatrick Skin Types IV, V, or VI, for the treatment of facial acne vulgaris.

Background

Acne vulgaris is a common skin disease characterized by inflammatory papules, pustules, and comedones that is prevalent in men and women of color. In fact, acne is the most common dermatologic diagnosis made in SOC populations (1). Although individuals of all skin types can develop acne vulgaris, there are important differences in darker skin types that are important to consider when choosing an optimal treatment (2).

From a diagnosis standpoint, acne in women of color is more likely to present on the cheek area, as opposed to a chin and cheek predominance in white women (2). Complications from acne are of great concern in this population, as women of color are more likely to develop keloids, hypertrophic scars, and post-inflammatory hyperpigmentation (PIH) as a result of acne lesions (3). PIH may last for weeks to months and, in many cases, is more troublesome to patients than the acne itself (2). Overall, facial acne and its sequelae have a greater impact on perception of appearance, negative emotions, and social functioning in women of color than white women (2).

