4. Subjects with a history of clinically significant hemolysis, anemia, or enteritis (regional enteritis, ulcerative colitis, pseudomembranous colitis, antibiotic-associated colitis)
5. Subjects with allergy or sensitivity to the study drug or its components
6. Subjects who have not complied with the proper wash-out periods:
 - a. Topical anti-inflammatory medications, salicylic acid, corticosteroids, antibiotics, antibacterials, peroxide-containing products, or retinoids within 2 weeks of baseline
 - b. Systemic antibiotics, corticosteroids, antimalarials or oral dapsone within 4 weeks of baseline

- c. Other anti-acne medication, including isotretinoin or spironolactone, within 6 months of baseline
 - d. Chemical peels or other facial acne procedures (laser therapy, light therapy) within 3 months of baseline
 - e. Treatment with botulinum toxin of any serotype in the face within 6 months of baseline
 - f. Estrogens/Birth control pills must have been started ≥ 90 days prior to baseline and use must be continued during the study without alteration or discontinuation.
7. Pregnant or breastfeeding.
 8. Subjects with evidence of alcohol or substance abuse.
 9. Use of any investigational drug within 4 weeks prior to randomization, or 5 pharmacokinetic/pharmacodynamic half-lives, if known (whichever is longer).

c) Number of Subjects

Up to 40 subjects with acne vulgaris will be screened with a goal of 20 total subjects randomized. All 20 randomized subjects are expected to complete all study procedures. Individuals who provide informed consent and fail to meet all of the inclusion and exclusion criteria during the initial evaluation will be considered a “screening failure.”

d) Study Timelines

The study will consist of 6 in-person visits and one phone visit (7 total visits) over up to 28 weeks (4 week screening period plus 24 weeks enrolled in study). Study visits will be conducted at Screening (Visit 1), Baseline (Visit 2, Week 0), Week 4 (Visit 3), Week 8 phone visit (Visit 4), Week 12 (Visit 5), Week 18 (Visit 6), Week 24 (Visit 7).

Enrollment will occur over a 24-36 month period from January 2018 to December 2020. The study is anticipated to be completed by December 2021.

e) Endpoints

Primary Endpoint:

1. Mean change from baseline to week 12 in Global Acne Assessment Score (GAAS)

Secondary Endpoints:

1. Change from baseline in Global Acne Assessment Score (GAAS) at week 4, 18, and 24.

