2. Change from baseline in Post Acne Hyperpigmentation Index (PAHPI) at weeks 12, 18, and 24.
3. Change from baseline in Melanin Index (MI) of target lesion at weeks 12, 18, and 24
4. Change from baseline in the proportion of subjects with score of 0 or 1 on ASIS “dark spot” score at weeks 4, 12, 18, and 24.
5. Proportion of subjects with GAAS of 0 (none) or 1 (minimal) at weeks 4, 12, 18, and 24

6. Percent change from baseline in all lesion counts (inflammatory, noninflammatory, and total) at weeks 4, 12, 18, and 24.

f) Procedures Involved in the Human Research

This is a single-center, single-group, open-label study using Aczone® (dapson) gel 7.5%. All subjects will receive the study medication. Aczone® gel is an off-white to yellow gel with suspended particles. It is supplied in an airless pump containing a polypropylene bottle with a high density polyethylene piston. It will be dispensed as a 60g pump.

Subject will apply Aczone® once daily to the entire face. Study drug must not be applied to other areas of the body, including the upper chest, upper back or shoulders.

Prior to the start of the study, potential subjects will be given an IRB-approved Informed Consent Document (ICD) containing a Health Insurance Portability and Accountability Act (HIPAA) disclosure agreement to read, understand, and sign. All questions about the study should be answered to the satisfaction of the candidate subject. They will have all of their study-related questions answered by the PI or designee, and if they agree to participate, the subject will sign two original copies of the ICD. The subjects will retain one original copy and one original copy will be kept in the study file. The subjects who sign an ICD will be assigned a screening number.

After providing informed consent, subjects will be assessed for study eligibility at the Screening visit (day -28 to day -1), which includes review of medical history and concomitant, acne lesion counting and severity ratings, and serum pregnancy test (if applicable). The PI or a medically qualified designee must review this information (i.e. medical history, concomitant medication, and eligibility review) for each subject to confirm their eligibility before enrollment. A total of 20 subjects who meet eligibility criteria will undergo Baseline / Day 0 assessments. Subjects will return for visits at weeks 4, 12, 18, and 24. There will be a phone visit at week 8.

Study Assessments and Efficacy Measures:

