Study drug is stored in a combination-locked room accessible only by clinical trials personnel. All study materials should be stored at room temperature (59°-77°F), and the Site is responsible for maintaining temperature logs. All study products received and dispensed will be inventoried and accounted for throughout the study. The investigator must maintain adequate records documenting the receipt, use, loss, or other disposition of the products on the Product Accountability Log. The log must identify the investigational product and account for its disposition by subject, including specific dates and quantities dispensed and returned. The log must be signed by the individual who dispensed/retrieved the study product and copies must be provided to the sponsor for inclusion in the Trial Master File.

At the completion of the study, all units of product dispensed (whether empty or containing unused product) must be collected by the Site and returned, along with un-dispensed product, to the Sponsor. Any container not returned by the Site must be accounted for in writing.

k) Statistical Analysis Plan

The adverse events will be tabulated according to their date of onset, duration, severity and relationship to the treatment. We will build Clopper-Pearson 90% confidence intervals for the proportion of adverse events considering their aggregation and stratification (e.g., by severity).

Sample Size Considerations

A sample size of $n=20$ subjects allows $>90\%$ power at 5% significance level for a two-sided paired t-test to detect at week 12 a minimum change in GAAS from baseline of 1 grade point. This calculation was performed in G*Power and it assumes a mean GAAS of 3.5 at baseline and a maximal standard deviation of 0.513.

Analysis of primary Endpoint

The primary analysis will apply a two-sided paired t-test to assess the significance of the change in GAAS from baseline to week 12. However, GAAS is an ordinal measurement and, for this reason, we will also apply a Generalized Linear Mixed-effects Model (GLMM) to assess the significance of the changes in GAAS after including potential covariates.

Analysis of secondary Endpoints

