At each time point, the changes from baseline in ordinal secondary endpoints GAAS, PAHPI, MI, the proportion of subjects with a score of 0 or 1 on ASIS “dark spot,” the proportion of subjects with $GAAS < 2$ will be presented in frequency tables. The (i,j) entries in the tables are counts of subjects in category i at baseline that moved to category j at that time point. A high frequency of counts falling off the main diagonal of the table is evidence in favor of a significant treatment effect. Similarly, to the primary endpoint, we will apply a two-sided paired t-test to assess the significance of changes from baseline in each outcome. We will apply the Bonferroni correction to adjust for the multiplicity of tests. In parallel, we will test pre vs. post differences in these ordinal outcomes with the Wilcoxon Signed Rank test. Discrepancies between the parametric and non-parametric approaches will be discussed on a case basis. In addition to this approach, we will fit an ordinal logit model, including all available time points, age, and gender as covariates.

The changes from baseline in lesion counts (inflammatory, non-inflammatory, and their aggregation) will be assessed with the two-sided paired t-test followed by Bonferroni correction. A Generalized Linear Mixed Model (GLMM) will be fitted to model the count of lesions as the dependent variable, time and inflammation as fixed effects, age, and gender as covariates. In this framework, we will include random intercept and slope for each subject’s trajectory. The contrasts will reveal differences between time points and treatment effect in inflammatory vs. non-inflammatory lesions.

Missing Data and Outliers

Missing data in the longitudinal data analysis will be handled by the mixed-effects approach which performs an appropriate adjustment of the coefficients’ degrees of freedom for each fitted model. We do not foresee issues with outliers due to the endpoints’ measurement level, most of them being ordinal.

Reference:

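### The study is single-group and open-label, so its tests show change from baseline; the SAP's secondary-endpoint text calls that change a treatment effect and should not

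*Combined protocol and SAP*

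**What the plan says.** Under Objectives: "The purpose of this study is to evaluate the safety and efficacy of Aczone" gel in adults with skin of color. Section f) describes the design: "This is a single-center, single-group, open-label study using Aczone" gel, with every subject receiving drug. Section e) defines the primary endpoint as the mean change in GAAS from baseline to week 12.

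Section k), under Analysis of primary Endpoint, states: "The primary analysis will apply a two-sided paired t-test to assess the significance of the change in GAAS from baseline to week 12". No null value is named, so the null is zero mean change. A GLMM is added because GAAS is ordinal. The sample size paragraph plans for 20 subjects "to detect at week 12 a minimum change in GAAS from baseline of 1 grade point", with more than 90% power, a baseline mean of 3.5 and a maximal SD of 0.513.

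Section k), Analysis of secondary Endpoints, goes further than change. It says that many counts off the main diagonal of a baseline-by-visit table support a significant treatment effect. Of the lesion-count model it says: "The contrasts will reveal differences between time points and treatment effect in inflammatory vs. non-inflammatory lesions".

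**The concern.** Without a control group or an external reference value, change from baseline is the sum of any drug effect and everything else that moves the score over 12 to 24 weeks. Several features of this protocol make some non-drug movement plausible. GAAS is rated by an unblinded investigator on a five-grade scale with descriptors such as few, several and many. Entry requires grade 3 or 4 at screening, and acne that is already regressing is eligible.

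The SAP does not acknowledge this limit. It gives a rule for reading the shift tables that turns movement into a treatment effect, and it applies the same term to a contrast between two lesion types in the same treated people. Because the objective is worded as efficacy, a reader of the final report could take a significant result as evidence that the drug works, which the design cannot supply.

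**Working it through.** **Inputs.** n = 20, two-sided 5%, planned change of 1 grade and SD 0.513 all come from Sample Size Considerations. The t critical value on 19 degrees of freedom is 2.093. The documents give no figure for non-drug improvement, so it is varied below as an assumption.

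**Step 1: the plan's own figure.** Noncentrality = (1 / 0.513) × √20 = 8.72. Noncentral-t power exceeds 99.9%, consistent with the stated figure of more than 90%.

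**Step 2: what 0.513 may be.** The text does not say whether it is the SD of the score or of the change. Twenty baseline scores split 10 at grade 3 and 10 at grade 4 have mean 3.5 and SD √(20 × 0.25 / 19) = 0.513, which matches both planning values. It therefore looks like a baseline SD. If both visits had that SD, the SD of change would be 0.513 × √(2(1 − ρ)). This is 0.513 at correlation ρ = 0.5 and 0.725 at ρ = 0. Because week-12 scores can range from 0 to 4, 1.0 is included as a wider assumption.

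**Step 3: smallest significant mean change.** Threshold = 2.093 × SD / √20.

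| SD of change | Threshold (grades) | Chance of significance if the whole change is non-drug: 0.2 grade | 0.24 grade | 0.5 grade |
|---|---|---|---|---|
| 0.513 | 0.24 | 38% | 51% | 98.5% |
| 0.725 | 0.34 | 22% | 29% | 83% |
| 1.0 | 0.47 | 14% | 17% | 57% |

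The thresholds run from about a quarter to just under half of the 1-grade planning change. With zero true change the rejection rate is 5.0%, as it should be.

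**Step 4: the shift-table rule.** As an illustration, suppose baseline is 10 subjects at grade 3 and 10 at grade 4. Five of the first move up to 4 and five of the second move down to 3. Ten of 20 counts are then off the diagonal, the mean change is (5 − 5) / 20 = 0, and the grade distribution is unchanged. The SAP's rule would read this as support for a treatment effect, because it does not distinguish improvement from worsening.

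**Step 5: the other analyses.** The GAAS GLMM and the secondary t-tests, Wilcoxon tests and ordinal model all estimate change over time in treated subjects. The lesion-type contrast compares change in one lesion type with change in the other. The two could follow different courses without the drug, so this contrast lacks a non-drug reference as well.

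**The case against.** The strongest reply is that the design is declared openly and the primary analysis is internally consistent. The endpoint is a mean change, the test is of that change, and the 5% level is correct for that hypothesis. This stands, and the primary test itself is not wrong.

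A reader might infer something stronger: that the plan declares efficacy about half the time when only a small non-drug improvement of about 0.24 grade is present. The documents do not support that.

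- No passage says that a significant primary p-value means efficacy. Both uses of treatment effect in the SAP concern secondary endpoints.
- Any such test rejects about half the time when the true change equals its significance threshold, so the one-half figure follows from choosing 0.24.
- A non-drug change of 0.24 is an assumption, and the figure also needs 0.513 to be the SD of change. At 0.725 the rate is 29% and at 1.0 it is 17%.
- Change is measured from a separate baseline GAAS rather than the qualifying screening score, which partly limits regression to the mean.

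A reader might also infer that the zero null must be replaced by a benchmark such as 0.5 grade. Nothing in the documents supports that value, and it would not isolate a drug effect. A non-drug change of 0.75 grade would exceed it by 0.25 and be significant 54% of the time at SD 0.513. With a true change of 1 grade, power against 0.5 is 98.5% at SD 0.513 but 83% at 0.725 and 57% at 1.0, the last two below the plan's stated level.

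What the reply does not answer is the secondary-endpoint wording. It states an inference that a single-group study cannot make.

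**Conclusion.** The point holds as one about interpretation. The primary and secondary analyses can establish change from baseline under open-label use; they cannot attribute it to the gel. The SAP's secondary-endpoint section says otherwise in two places, and its shift-table rule also counts worsening as supporting evidence. That conclusion follows from the design and the text and needs no numerical assumption.

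The numbers only give scale. A mean GAAS change of 0.24 to 0.47 grade, for SDs of change from 0.513 to 1.0 and all 20 subjects completing, is enough for significance against a planning change of 1 grade. A significant p-value alone therefore says little about whether the change reached the planned size. How much of any change would be non-drug cannot be determined from the documents.

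**What to change.** 1. Section k), Analysis of secondary Endpoints: replace both uses of treatment effect (including the one qualified as significant) with change from baseline. Report improvement and worsening separately in each shift table.
2. Section k), Analysis of primary Endpoint: make the mean week-12 GAAS change with its 95% confidence interval, set beside the 1-grade planning target, the primary reported result. State that a significant test against zero shows change from baseline under open-label use and not a drug effect.
3. Optional: test against a non-zero benchmark, only if the sponsor can justify a value before analysis and states the power against it.

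Items 1 and 2 change SAP wording and reporting only, with no new subjects, visits or data. The downside is a more modest claim.

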Global Acne Assessment Score (GAAS):

The subject's acne severity will be assessed by the investigator using a 5-point GAAS at screening, baseline, and weeks 4, 12, 18, 24.

Grade	Description
0	None No evidence of facial acne vulgaris
1	Minimal Few noninflammatory lesions are present; a few inflammatory lesions (papules/pustules) may be present; no nodulo-cystic lesions present
2	Mild Several to many noninflammatory lesions are present; a few inflammatory lesions are present; no nodulo-cystic lesions present.
3	Moderate Many noninflammatory and inflammatory lesions are present; no nodulo-cystic lesions are present.
4	Severe Significant degree of inflammatory disease; papules and pustules are a predominant feature; a few nodulo-cystic lesions are present (no more than 2)

Lesion Counts:

The lesion counts, including inflammatory and non-inflammatory lesions, will be performed at screening, baseline, and weeks 4, 12, 18, and 24. Inflammatory lesions (papules, pustules, nodules/cysts) and

noninflammatory lesions (open comedone, closed comedone) will be counted individually. The sum of the inflammatory lesion counts and non-inflammatory lesion counts will be totaled.

ASIS ®:

Acne Symptom and Impact Scale (ASIS ®) will be given to subjects' for completion at baseline and weeks 4, 12, 18, and 24. The ASIS ® contains 9 items assessing symptom severity and 8 items assessing the psychosocial impact of acne vulgaris (6). High scores on the ASIS® indicate the presence of more severe symptoms, whereas higher scores on the ASIS indicate better outcomes on acne health-related quality of life.

PAPHI:

The postacne hyperpigmentation index (PAHPI) has been shown to be a reliable and valid score measuring post-inflammatory hyperpigmentation from acne (7). PAHPI will be scored using the following formula:

Total PAHPI = S + I + N

PAHPI Score can range from 6-22.

Lesion Size (S)

Weighted Score (S)	Median Lesion size
2	<3mm
4	3-6mm
6	7-10mm
8	>10mm

Lesion Intensity (I)

Weighted Score (I)	Median Lesion Intensity
3	Slightly darker than surrounding skin
6	Moderately darker than surrounding skin
9	Significantly darker than surrounding skin

Lesion Number (N)

Weighted Score (N)	Number of Lesions
1	1-15
2	16-30
3	31-45

4	46-60
---	-------

5	>60
---	-----

Melanin Index:

A narrowband reflectance spectrophotometer (mexameter MX-16) will be used to measure the degree of pigmentation of involved and adjacent uninvolved skin of one representative facial PIH lesion (8).

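### The shift-table sentence reads a directionless off-diagonal count as a treatment effect in a single-group study, and MI enters those tables as ordinal with no categories defined (minor)

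*Combined protocol and SAP*

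**What the plan says.** Under *k) Statistical Analysis Plan, Analysis of secondary Endpoints*, the frequency tables cover "the changes from baseline in ordinal secondary endpoints GAAS, PAHPI, MI, the proportion of subjects with a score of 0 or 1 on ASIS" (meaning its item on dark spots), and the proportion with GAAS below 2. The table is defined in one sentence, "The (i,j) entries in the tables are counts of subjects in category i at baseline that moved to category j at that time point", and the next says how to read it: "A high frequency of counts falling off the main diagonal of the table is evidence in favor of a significant treatment effect". No threshold is given, and cells above and below the diagonal are not separated.

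The same paragraph then plans the formal inference. First, "we will apply a two-sided paired t-test to assess the significance of changes from baseline in each outcome", with Bonferroni correction. In parallel, "we will test pre vs. post differences in these ordinal outcomes with the Wilcoxon Signed Rank test". Finally, "we will fit an ordinal logit model, including all available time points, age, and gender as covariates".

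Two other places bear on this. *f) Procedures Involved in the Human Research* states: "This is a single-center, single-group, open-label study". The *Melanin Index* section describes an instrument reading: "A narrowband reflectance spectrophotometer (mexameter MX-16) will be used to measure the degree of pigmentation of involved and adjacent uninvolved skin". GAAS grades and the PAHPI component scores are tabulated in *Study Assessments and Efficacy Measures*. No categories or cut-points for MI appear anywhere.

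**The concern.** Three things are wrong with the sentence and the list that it governs.

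1. **Direction.** A subject leaves the main diagonal by moving either way. A table with balanced movement can be as full off the diagonal as one showing clear improvement.
2. **Attribution.** With one open-label group, a net favourable shift mixes any drug effect with natural course, regression to the mean after selection on GAAS 3 or 4, and unblinded rating. The tables can show change from baseline and nothing more.
3. **MI.** A category-by-category table needs categories. Because none are defined for MI, someone must choose them later, and the off-diagonal count then depends partly on that choice.

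At stake is what the report may say about the secondary tables. A sentence written into the SAP can be cited as the pre-specified way to read them, alongside paired tests that show no such effect. Hyperpigmentation is one of the study's declared interests, so the MI table is likely to be read.

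**Working it through.** The SAP gives no figure for this rule, so there is none to reproduce. The check uses the SAP's planning values to see whether the rule separates tables that differ in direction.

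**Inputs from the documents.** n = 20 (*c) Number of Subjects*). GAAS runs from 0 to 4, with 3 or 4 required at screening. The planning mean is 3.5 and the SD 0.513 (*Sample Size Considerations*). Ten subjects at grade 3 and ten at grade 4 give exactly this: mean 3.5, SD = √(20 × 0.5² / 19) = √(5/19) = 0.513. On that split at most 10 subjects can worsen.

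**Step 1: direction.** Take one-grade moves with *a* improved, *b* worsened and the rest unchanged. The mean change is (b − a)/20, the variance is [(a + b) − 20 × mean²]/19, and t = mean / (SD/√20) on 19 degrees of freedom. When all moves are one grade, the exact signed-rank test is a binomial test on the movers. The p-values are unadjusted.

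| Improved / worsened | Off diagonal | Mean change | SD | t | t-test p | Exact signed-rank p |
|---|---|---|---|---|---|---|
| 12 / 2 | 14 of 20 | −0.5 | √(9/19) = 0.688 | −3.25 | 0.004 | 0.013 |
| 7 / 7 | 14 of 20 | 0 | √(14/19) = 0.858 | 0 | 1.0 | 1.0 |
| 4 / 10 | 14 of 20 | +0.3 | √(12.2/19) = 0.801 | 1.67 | 0.11 | 0.18 |

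All three tables are 70% off the diagonal, so the SAP sentence reads them alike. The SAP's own tests do not.

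**Step 2: where direction matters.** Eligibility puts almost everyone outside the GAAS-below-2 category at baseline, so movement in that table is essentially one way and pooling matters little. For GAAS itself, the only possible worsening from entry is 3 to 4. PAHPI, MI and the ASIS dark spot item have no entry restriction and can move either way, so pooling matters mainly there.

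**Step 3: MI.** Assume no true change, independent error with SD *s* on each reading, true values spread evenly within categories, and category width *w*. Neither *s* nor *w* is in the documents. The difference D between two readings is normal with SD σ = s√2, and two readings fall in different categories with probability min(|D|/w, 1). The expected count is therefore

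20 × { σ√(2/π) × [1 − exp(−w²/2σ²)] / w + 2[1 − Φ(w/σ)] }.

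For s = 5, σ = 7.07 and σ√(2/π) = 5.642:

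- w = 1: 20 × (0.056 + 0.888) = 18.9
- w = 10: 20 × (0.357 + 0.157) = 10.3
- w = 50: 20 × (0.113 + 0.000) = 2.3

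Over a range of assumed SDs:

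| Category width | s = 2 | s = 5 | s = 10 | s = 20 |
|---|---|---|---|---|
| 1 | 17.2 | 18.9 | 19.4 | 19.7 |
| 10 | 4.5 | 10.3 | 14.6 | 17.2 |
| 50 | 0.9 | 2.3 | 4.5 | 8.7 |

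About half of each count lies on each side of the diagonal. With no real change, the table can look full or nearly empty of movement depending on a width that the SAP does not give.

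**The case against.** The strongest reply is that the sentence is not a decision rule. It speaks only of evidence, sets no threshold, and leaves significance to two-sided paired t-tests with Bonferroni correction and to signed-rank tests, all of which use direction. That stands. A reader might infer that the plan would declare secondary endpoints significant on table counts alone; the documents do not support this, and no planned test result changes.

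A reader might also infer that any net worsening would count as an effect against the plan's own tests. That goes too far. The tests are two-sided, so strong worsening is significant as well: 0 improved and 10 worsened gives t-test p=0.0003 (signed-rank 0.002), and 2 and 10 gives 0.017 (0.039), unadjusted. The contradiction is confined to balanced or mildly net-worse tables. Strong worsening is a detectable change, but it is not benefit.

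The GAAS examples are extreme. On the ten-and-ten split, 4/10 needs every grade-3 subject to worsen, and entry requires acne that is stable or regressing. They show the arithmetic, not a likely result.

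The p-values are also unadjusted. If the Bonferroni family were the 17 endpoint-visits in that paragraph (GAAS 3, PAHPI 3, MI 3, ASIS 4, GAAS 0/1 4), the threshold would be 0.05/17 = 0.0029 and even the 12/2 table (p=0.0042) would miss it. The SAP does not state the family. The contrast between the three tables does not depend on it.

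For MI, a reader might infer that the ordinal logit cannot be fitted either. It can: a cumulative logit may treat each distinct value as a level, so the width argument applies to the table only. What remains against the logit is that it is an odd choice for an instrument reading.

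**Conclusion.** The point holds as a minor one. As written, the sentence is wrong: an off-diagonal count cannot tell improvement from worsening, and with one group no table can show a treatment effect. The practical error is that balanced or mildly net-worse tables would be read as an effect that the paired tests do not show. It bears mainly on PAHPI, MI and ASIS dark spot.

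The MI label is also wrong for a spectrophotometer reading, and its table cannot be built without a later choice of categories. That conclusion rests on the documents alone. The sizes quoted for it (18.9, 10.3 and 2.3 of 20) rest on an assumed reading SD of 5 units, assumed widths and no true change. They show dependence on the width and do not predict the trial's data.

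Harm is limited to the reading of the secondary tables and the choice of model for MI. The primary analysis and the planned paired tests are unaffected.

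**What to change.** (a) Replace the off-diagonal sentence with: *For each table we will report the numbers improved, unchanged and worsened; net direction will be judged by the planned paired tests, and results will be described as change from baseline.*

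(b) Remove MI from the ordinal list and from the shift tables. Analyse it as continuous with the planned paired t-test, keeping the planned signed-rank test as a check. Replace its ordinal logit with a linear mixed model using all MI visits (baseline, weeks 12, 18 and 24), age and gender, with a subject random intercept. Removing MI from the ordinal logit without this replacement would leave it with no model across visits. The mixed model also fits the approach in *Missing Data and Outliers*.

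The cost is SAP wording and one substituted model, with no new data, visits or subjects. MI loses its shift table, and the tables can no longer be cited as evidence of a treatment effect. No planned paired test is dropped.
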